5.4 Standard Calculations

Variables requiring calculation will be derived using the following formulas:

- **Study day** – For a given date (*date*) on or after successful IUS insertion (*iusindt*), study day is calculated as:

$$\text{Study day} = \text{date} - \text{iusindt} + 1$$

For a given date (*date*) prior to successful IUS insertion (*iusindt*) or for subjects with failed insertion, study day is calculated as:

$$\text{Study day} = \text{date} - \text{iusindt}.$$

The day of successful IUS insertion is Study Day 1 and the day prior to IUS insertion is Study Day -1. There is no Study Day 0

Months – A duration expressed in months is calculated as the number of completed calendar months plus the proportion of any partial month completed. A month is calculated using the following formula: Duration in months = (date2-date1)/30.4

- **Years** - A duration expressed in years between one date (*date1*) and another later date (*date2*) is calculated using the formula noted below:

$$\text{Duration in years} = (\text{date2}-\text{date1})/365.25$$

- **Age** - Age is calculated as the number of years from the date of birth (*DOB*) to the IUS insertion attempt date (*iusindt*). For displaying a subject's age, the following formula is used:

$$\text{Age (years)} = \text{floor}(\text{insertion attempt date} - \text{birthdate})/365.25$$

- **Body Mass Index (BMI)** - BMI is calculated using height (in cm) and weight (in kg): $\text{BMI (kg/m}^2\text{)} = \text{weight (kg)} / [\text{height (cm)} / 100]^2]$

- **Cycles of Use** – Cycles are calculated using the date the IUS was expelled/removed (from the IUS Discontinuation CRF). Total use duration expressed as the number of 28-day cycles is defined as (IUS expulsion/removal date - date of IUS insertion (*iusindt*)+1)/28. If the expulsion/removal date is unknown then:

- Subjects who are still on treatment will have their last known date of product use used in the cycle calculations in lieu of an IUS expulsion/removal date, derived as follows: For the evaluation of safety, the last known date of product use will be the last date of on-study contact with the subject where she reported that the IUS is still in place or the last date at which a pregnancy

test was performed (at study site or outside laboratory with copy of report), whichever is later. For the evaluation of efficacy, the last date at which a pregnancy test was performed will be used (at study site or outside laboratory with copy of report).

- If, during on-study contact with the subject (e.g., Month 9 Contact, Month 15 Contact, Month 21 Contact), she reports that the IUS is no longer in place, the date of contact minus 1 day or last date at which a pregnancy test was performed (at study site or outside laboratory with copy of report), whichever is later, will be used as the last date associated with IUS use.
- Subjects who become pregnant with the IUS still in place will have their estimated date of conception used as the last IUS use date.
- In the cases of subjects who are lost to follow-up or withdraw consent prior to IUS removal and neither a last contact date nor a last pregnancy test date is available, the IUS insertion date + 1 day will be used as the last date associated with IUS use.

Similarly, for subjects who had a successful IUS insertion but who have not yet had any post-insertion data (e.g., diaries or post-insertion pregnancy test results) retrieved at the site which could be used to directly calculate duration of use, the IUS insertion date +1 day will be used as the last date of IUS use for the purpose of analysis. For the summary of duration of product use, all subjects with ≥ 1 days of product use, as defined in this section, will be included in the calculations. For the evaluation of adverse events, subjects with less than one calculated complete 28-day cycle of use (at least 23 days) will be excluded unless such subjects reported an adverse event at any time during the first 28 days following IUS insertion (see Section 11.2: Adverse Events for more detail).

5.5 28-Day Cycles of Use Calculation for Efficacy Evaluation

In addition to the calculation of 28-day cycles based on last date of IUS use as described in Section 5.4, the efficacy evaluation requires the exclusion of cycles from the Pearl Index denominator where the use of other birth control methods was reported. Since this information is obtained exclusively from subject daily diaries, 28-day cycles of use need to be calculated from the diary data so as to be able to determine when the use of other birth control methods occurred.

Using the same algorithm described in Section 5.4, each recorded diary date between the IUS insertion date and the last calculated date of product use, inclusively, is compared to the IUS insertion date in order to calculate cycle number and day. Duration of use expressed as the number of 28-day cycles is then calculated as the maximum duration

(ceiling value) between the IUS insertion date and last recorded diary date. The number of cycles where other birth control methods were used can be calculated directly since each recorded diary record is associated with a cycle number and day.

If the last cycle obtained using either the method described in Section 5.4 or the diary-based method described here has fewer than 23 days, that cycle is considered incomplete and is excluded from the counting process of the number of complete 28-day cycles (see Section 9.2: Primary Efficacy Variable for additional discussion). In addition, if the cycle counts obtained using the method described in Section 5.4 and this section result in different estimates for the number of completed cycles (usually because a subject has stopped completing the diary short of her last site visit or pregnancy test), the smaller of the two calculations will be used. This is a conservative approach that preserves the integrity of the available data as the basis of cycle derivation.

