Eligible subjects for the efficacy evaluation of LNG20 will include a minimum of approximately 1600 subjects 16-35 years of age using LNG20. In the original protocol, approximately 650 LNG20 and 160 Mirena subjects were randomized at a 4:1 ratio of LNG20 to Mirena. In the amended single-arm protocol currently in force, the remaining approximately 950 subjects will be assigned to LNG20 only. The 1600 LNG20 subject total represents the combined LNG20 exposure in women aged 16-35 under protocol versions 1.0 through 4.0 using the original inserter and protocol versions 5.0 and later utilizing the redesigned LNG20 inserter. Subjects in the Treatment PK substudy (approximately 60) will be assigned by the IVRS separately from the remainder of study subjects based on BMI. An additional 150 eligible females 36-45 years of age will receive LNG20 as part of a non-randomized cohort to provide additional safety and tolerability information, since IUSs are used with relative frequency by women over the age of 35.

Subjects who discontinue treatment for any reason will not be replaced.

After consent is obtained, screening procedures will be performed and eligible subjects enrolled into the trial via an Interactive Voice Response System (IVRS). Enrollment and IUS insertion may occur on the same day as the screening procedures. The assigned IUS will be inserted by a study Investigator using standardized procedures specific to each system.

LNG20 subjects will be evaluated during study treatment use for up to 85 months (Mirena subjects for up to 60 months). Study assessments will be performed at a clinic visit at Screening/Enrollment and Months 1, 3, 6, 12, 18, 24, 30, 36, 42, 48, 54, 60, 66, 72, 78, 84, 90, 96, 102, 108, 114, 120 and 121 (Mirena subjects only through Month 60 and LNG20 36-45 years old subjects only through Month 96). Telephone assessments will occur at 3 month intervals between scheduled study visits, starting at Month 9. The IUS will be removed when requested by the subject, when clinically indicated, when requested by investigator or sponsor, or at the end of 121 months of use (60 months for Mirena subjects and 96 months for LNG20 36-45 years old group).

All subjects will have a follow-up safety visit one month after discontinuing the study treatment. Additional follow-up will be conducted for subjects who:

- Have an ongoing IUS or IUS procedure-related adverse event

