6. ANALYSIS POPULATIONS

The Safety population will include all subjects enrolled who underwent the IUS insertion procedure, regardless of age and outcome. Treatment assignment will be based on the treatment actually received.

The following subject populations will be used for efficacy analyses:

- Modified Intent-to-Treat (MITT) population will include all subjects between 16 and 35 years of age at study entry for whom the assigned IUS is successfully

placed in the uterus and for whom there is at least one assessment of pregnancy status after inserting the IUS.

- Per-Protocol (PP) population will include subjects in the MITT population with no major protocol deviations (to be identified prior to database cut-off).

The Treatment Pharmacokinetics (PK) population will include all subjects enrolled in the substudy and have at least one post-insertion PK assessment and no major protocol deviations.

The Elimination PK population will include all subjects enrolled in the substudy (who will be randomized to one time point post-IUS removal) and whose post-IUS removal PK assessment is not missing. The elimination PK sampling will only be obtained at the full intended duration of use IUS removal visit (i.e. Month 121).

The Endometrial Thickness (ET) population will include all subjects enrolled in the ET substudy and have at least one post-insertion ET measurement. The final endometrial thickness measurements will be obtained at baseline, Month 12, Month 60 and after the full intended duration of use (i.e. 10 years).

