11. SAFETY ANALYSIS

All safety analyses will be based on the Safety population.

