11.2 Adverse Events

Menstrual bleeding and cramping/pain for the first 24 months are recorded in a daily subject diary and not on the Adverse Events CRF (unless the event is an SAE, results in IUS removal or is not related to the IUS or menstrual condition). The subject daily diary has been designed to collect IUS and menstrual bleeding and cramping AEs following insertion of the study IUS. Menstrual bleeding or cramping/pain would only be entered onto the general AE CRF if:

- Bleeding or cramping/pain meet serious criteria; an SAE report would also have to be submitted (this exception is due to data system requirements)
- Bleeding or cramping/pain result in the IUS being removed (this exception is due to data system requirements)
- Bleeding or cramping/pain is not related to the IUS or a menstrual condition.

After 24 months, menstrual bleeding and cramping/pain are recorded on the Adverse Events CRF. Analyses of cramping/pain and bleeding are described below in section 11.6 .

All adverse event summaries will be restricted to treatment-emergent adverse events (TEAE), defined as AEs occurring during or after attempted IUS insertion and those pre-attempted IUS insertion existing medical conditions that worsened during the study up to the subject's last known IUS date of use or, for subjects who have discontinued, through 30 days after the subject's last known IUS date of use. If an AE cannot be determined as treatment-emergent, it will be counted as such.

Verbatim terms on case report forms will be mapped to preferred terms and system organ classes using the Medical Dictionary for Regulatory Activities (MedDRA) dictionary. Each adverse event summary will be displayed by treatment group. Summaries that are displayed by system organ class and preferred terms will be ordered by descending order of incidence of system organ class and preferred term within each system organ class. Summaries of the following types will be presented:

- Overall subject summary of AEs, SAEs, and deaths
- Subject incidence of TEAEs and total number of unique TEAEs by MedDRA system organ class and preferred term.
- Subject incidence of TEAEs by MedDRA system organ class, preferred term, and highest severity. At each level of subject summarization a subject is classified according to the highest severity if the subject reported one or more events. AEs with missing severity will be considered severe for this summary

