- Subject incidence of TEAEs by MedDRA system organ class, preferred term, and closest relationship to IUS (Related/Not Related). At each level of subject summarization a subject is classified according to the closest relationship if the subject reported one or more events. Related will be defined as “Related”, “Probably Related”, or missing. Not related will be defined as “Unlikely Related” or “Not Related”
- Subject incidence of TEAEs by MedDRA system organ class, preferred term, and closest relationship to IUS Procedure (Related/Not Related). At each level of subject summarization a subject is classified according to the closest relationship if the subject reported one or more events. Related will be defined as “Related”, “Probably Related”, or missing. Not related will be defined as “Unlikely Related” or “Not Related”
- Subject incidence of serious TEAEs and total number of unique serious TEAEs by MedDRA system organ class and preferred term

Incidence rates will include in the denominator all subjects in the Safety Population.

Missing Severity or Relationship

Missing severity or relationship to study drug will prompt queries to be sent to the investigators to provide the information. If after query resolution, the information remains missing, the following conventions will be used in summary tables.

- An event with missing severity will be considered Severe.
- An event with missing relationship will be considered related to study drug.

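### SAP 5.4 keeps women with under 23 days of use in the adverse event evaluation only if they had an early event, which conflicts with SAP 11.2; secondarily, the general AE tables set crude incidence side by side over unequal durations of use

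*SAP*

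**What the plan says.** **Who counts in the AE evaluation.** SAP 5.4 (Cycles of Use) treats a cycle as complete from 23 days. Women with less use than that "will be excluded unless such subjects reported an adverse event at any time during the first 28 days following IUS insertion"; for more detail it sends the reader to 11.2. Section 11.2 contains no such rule and says "Incidence rates will include in the denominator all subjects in the Safety Population". SAP 11 opens with "All safety analyses will be based on the Safety population", and SAP 6 defines that population: "The Safety population will include all subjects enrolled who underwent the IUS insertion procedure, regardless of age and outcome".

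**The window for treatment-emergent events.** SAP 11.2 counts events up to last known use or, "for subjects who have discontinued, through 30 days after the" last known date of use.

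**Women without data.** The paragraph in 5.4 that holds the exclusion also says that, where an insertion succeeded but no post-insertion data have been retrieved, "the IUS insertion date +1 day will be used as the last date of IUS use for the purpose of analysis".

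**The AE tables.** They give subject incidence, and "Each adverse event summary will be displayed by treatment group". SAP 5.1 names three groups for safety summaries: LNG20 16-35, LNG20 36-45 and Mirena. SAP 3 ends use "at the end of 121 months of use (60 months for Mirena subjects and 96 months for LNG20 36-45 years old group". SAP 3 keeps the Mirena data as an informative comparator in a short list of tables that includes AE incidence. Woman-years are tabulated by group in SAP 8.2, apart from the AE tables.

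**The concern.** **(a) Main point.** An exclusion that is lifted when the woman has an event selects on the outcome. Among short-use women, everyone retained has an AE by construction. The rule also contradicts three other places in the same SAP, so two programmers could produce different denominators and each cite the plan. The precedence clause in SAP 1 settles conflicts between SAP and protocol; it does not help when both texts are in the SAP.

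**(b) Secondary point.** Subject incidence on a head-count denominator grows with time at risk. Where one column can run to 121 months and its neighbour to 60, equal risk gives unequal percentages. No test is planned, so the percentages themselves are what a reader will compare.

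**Working it through.** **(a) The two rules side by side**

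Take a woman whose last use is day 22, counting insertion as day 1.

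1. Use is under 23 days, so 5.4 applies to her.
2. Her treatment-emergent window ends on day 22 + 30 = 52.
3. An AE in the first 28 days keeps her in under 5.4.
4. A first AE on days 29 to 52 is treatment-emergent under 11.2, but under 5.4 she leaves both numerator and denominator.
5. With no AE, she stays in the denominator under 11.2 and leaves it under 5.4.

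Let p be the percentage of women with an AE in the full Safety Population, x the share dropped by 5.4, and b the fraction of the dropped women who had a first event after day 28 but within the window. The reported percentage becomes

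q = (p − x·b) / (1 − x).

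It rises if b < p and falls if b > p. With b = 0 the factor is 1/(1 − x):

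- x = 1%: 1/0.99 = 1.01
- x = 5%: 1/0.95 = 1.05

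Both values of x are assumptions, because the documents give no count of women with under 23 days of use. The second is hard to credit. Protocol 7.1.3 cites expulsion of 3.1% to 4.5% over a whole year, whereas x covers 23 days and only women without an early AE.

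**(b) Unequal time at risk**

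Inputs from SAP 4: annual discontinuation ceilings of 20%, 19%, 17%, then 16% in each of years 4 to 10, and a stated 10-year total of 76%. The stated total does not follow from the annual figures: 1 − 0.80 × 0.81 × 0.83 × 0.84^7 = 84.1%. I therefore ran both versions. The second multiplies every annual discontinuation hazard by ln(1/0.24) / ln(1/0.159) = 0.775, so that the total is 76%.

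Assumptions: the same event hazard in both groups, and LNG20 discontinuation applied to Mirena as well. With event hazard λ, discontinuation hazard g = −ln(1 − d) and S the share still at risk at the start of a year, each year adds

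S · λ/(λ + g) · (1 − exp(−(λ + g)))

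to the incidence, and S is then multiplied by exp(−(λ + g)).

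| Assumed hazard per 100 woman-years | Month 60 | Year 10 | Ratio | Ratio, rescaled to 76% |
|---|---|---|---|---|
| 2, constant | 6.0% | 8.2% | 1.37 | 1.45 |
| 5, constant | 14.1% | 18.5% | 1.32 | 1.39 |
| 10, constant | 25.5% | 31.8% | 1.25 | 1.30 |
| 5 in year 1, then 1 | 6.5% | 7.6% | 1.18 | 1.22 |
| 3.15 in year 1, then 0.71 | 4.3% | 5.1% | 1.19 | 1.25 |
| 4.5 in year 1, then 0.35 | 4.7% | 5.1% | 1.09 | 1.11 |

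The incidences shown use the stated annual ceilings. The last two rows take their shape from the expulsion figures in Protocol 7.1.3 (3.1% or 4.5% at one year, 5.8% at 60 months). They serve only as a front-loaded pattern, because SAP 11.9 already reports expulsion at common times.

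A single rate pooled over all use does not remove the problem when risk is front-loaded. With 5 then 1 per 100 woman-years, the pooled first-event rate is 2.19 to month 60 and 1.86 to year 10, although the hazards are identical. Rates are needed by year of use.

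SAP 3 also gives 85 months of evaluation for LNG20, in the same paragraph as 121 and 96. Those figures must be reconciled, but all of them exceed Mirena's 60.

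**The case against.** **On (a).** Three places in the SAP say full Safety Population, and the lone contrary sentence sits in a section on deriving cycles, so a programmer would probably follow 11.2. The aim may have been only to set aside women with no post-insertion data. Many causes of very early discontinuation are themselves AEs: bleeding or pain that leads to removal goes on the AE form (Protocol 7.12.1, SAP 11.2), and Protocol 7.3 and 7.13 treat expulsion as an adverse event. Those women stay in. All of this stands, and it limits the size. It does not resolve the conflict, because the sentence as written also catches women with known short use and defers to detail that is absent.

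A reader might infer that 5.4 inflates AE percentages materially or in a fixed direction. The documents do not support that: x is not given, and the direction depends on b against p. A reader might also extend the rule to failed insertions. The point here does not rest on them; it concerns women with a successful insertion and short use.

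**On (b).** Crude incidence beside a woman-years table is a coherent descriptive display, and no passage contradicts it. Mirena is informative only, and SAP 5.1 and 5.6 rule out testing. Time-aligned summaries already exist for continuation, expulsion and safety-related removal (SAP 11.9), and bleeding and cramping are summarised by cycle and interval, then three-monthly (SAP 11.6). This stands, and it makes (b) an improvement, not an error. What remains is that other AEs have no such summary.

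A reader might infer that at early rolling submissions the difference reverses, so that LNG20 looks better. With staggered entry assumed uniform from November 2009 to April 2013, that appears clearly only at a cut-off about 5 years after first enrolment, in November 2014. By 8 years, November 2017, the ratio is already 1.02 to 1.16. The protocol is dated October 2017 and this SAP incorporates its Version 9, so a reversal is not a consequence of this plan.

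**Conclusion.** **(a) is wrong as written.** SAP 5.4 makes inclusion in the AE evaluation depend on having had an AE, contradicts SAP 6, 11 and 11.2, and can lose treatment-emergent events that begin after day 28. The size is unknown and probably small: a factor of 1.01 if 1% of women are dropped and none has a later event, both assumed.

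**(b) is a secondary and inexpensive improvement.** At identical risk, LNG20 16-35 incidence at year 10 is about 1.1 to 1.45 times Mirena incidence at month 60. The range rests on assumed hazards and on applying LNG20 discontinuation to Mirena. It applies to events that accrue over time; events confined to insertion would be little affected. A reader might conclude that the planned AE tables are invalid; the documents support only that they need a time-aligned companion.

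**What to change.** 1. Delete the exclusion sentence in SAP 5.4 and use the full Safety Population as in 11.2. If women with no post-insertion data are to be set aside, define them by absence of data, not by AE status, and do so only in a sensitivity table.
2. For the LNG20-Mirena AE displays in SAP 11.2, add one table at overall and system-organ-class level, with both groups truncated just before the month-60 completion visit. Give subject incidence, and events per 100 woman-years by year of use. Truncating after that visit would count Mirena end-of-use removal events, reportable under Protocol 7.14, against continuing LNG20 use. The alternative is to show removal-procedure and post-removal events separately.
3. Report later LNG20 AEs per 100 woman-years by year of use, not as one pooled rate.
4. Note under the table that about 950 LNG20 women were not randomised against Mirena, so the display stays descriptive. At any cut-off before all LNG20 women could have reached month 60 (April 2013 plus 60 months, so April 2018 on the planned dates), truncation alone does not equalise time at risk, and the by-year rates are the ones to read.

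Cost: one sentence deleted, one table and a set of by-year rates added, no new data. The AE section becomes slightly longer.
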